***Observe quality and performance indicators among usual oncology care in similar patient-caregiver population to compare with cases.*** From non-treatment sites, identify, recruit, consent, and enroll persons with lung cancer (newly diagnosed or recent recurrence of disease) and their caregivers into the evaluation study. Recruitment will continue until 25 patients and 25 caregivers are enrolled (Control Dyads). Electronic health records for patients (appointment, clinical, and patient-reported data such as the M.D. Anderson Symptom Inventory that is standard of care) and study questionnaires will be used to evaluate quality and performance indicators however, questionnaires will be fielded at the post-period only. Non-treatment sites will not provide FCA as standard of care and function as control sites. These sites will include Geisinger Wyoming Valley in Wilkes-Barre, PA (“GWV”), and Geisinger Community Medical Center in Scranton, PA (“GCMC”). A case-matched controlled design will be used to evaluate differences in quality and performance indicators between groups at the post-period only.

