#### **4.2.1 Approximate Number of Subjects**

Approximately 135 Geisinger subjects (65 patients and 50 caregivers) will participate in the study. Patients are able to participate independent of having a caregiver; therefore the number of Geisinger patients enrolled is reflective of this possibility. Our goal is to include 100 participants in our analysis (50 patients and 50 caregivers) organized as 25 Cases Dyads and 25 Control Dyads. We will enroll 20 Geisinger providers in the treatment site who will participate in this study. If a caregiver receives care at Geisinger, his/her patient-related records are not of interest to or related to this study.

Background Logic Regarding Sample Size: The number of eligible lung cancer patients was estimated from a twelve-month report (May 2016-April 2017) ("Estimate Time Period") from each respective hospital which informed the Exploratory Evaluation Study design. Patients were included if, during the Estimate Time Period, they had an active lung cancer diagnosis on the EHR problem list and had an encounter at one of the following oncology departments (Hematology Oncology Danville, Radiation Oncology Danville, Hematology Oncology GWV, Radiation Oncology GWV) ("Inclusion Criteria"). There were 153 eligible patients from GMC ("GMC Lung Cancer Patients"), 137 eligible patients from GWV ("GWV Lung Cancer Patients"), and 21 eligible patients from GCMC ("GCMC Lung Cancer Patients") for potential inclusion in the Exploratory Evaluation Study and Phase III FCA expansion rollout. Given that the Exploratory Evaluation Study period is 6 months, the estimated count of eligible patients is reduced by 50% to 77 Case patients at GMC, 69 Control patients at GWV and 11 Control patients at GCMC.

Based upon Phase II enrollment at GMC, it is anticipated that 37% of eligible GMC Lung Cancer Patients (i.e., 28) will consent to participate in the evaluation and enroll as a Dyad. Based on Phase II enrollment at GMC, 100% of these patients will identify a caregiver who consents to

*Version 1.10 – 5.24.2018*

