For every Case patient enrolled at GMC, a data analyst will run the algorithm to consume aggregate electronic health record data to find and create a database of potential participants that meet inclusion (and do not meet exclusion) criteria at control sites. A weekly occurrence of the eligibility list will occur however, depending on the rate of recruitment the study team will determine whether this needs to occur more frequently. Study team members will apply a 1:1 case-matched control strategy to identify potential control patients that match case patients in terms of sex, age category, lung cancer histology, and lung cancer clinical and/or pathological staging information. This will be done after the Case patient-participant has a Case caregiver-participant consented to ensure that Case Dyads are enrolled and available for matching. If a Case patient-participant has enrolled but the Case caregiver-participant fails to enroll, the Case patient-participant will still be eligible for the study however the study team will recruit a replacement Case Dyad with the goal of enrolling 25 Case Dyads. Case patient-participants without caregiver-participants will be removed from analyses. Similarly, if a Control patient-participant consents but a Control caregiver-participant fails to enroll, the study team will identify a replacement Control Dyad with the goal of enrolling 25 Control Dyads. Research assistants will use the database to run weekly reports to identify potential control patients at GCMC or GWV to approach for recruitment. The research assistants will verbally review the list of potential participants as well as the weekly MDC list at GCMC and GWV with clinical staff to validate that patients on the list meeting inclusion criteria and can be approached for recruitment. The research assistant will be available to speak with patients before or after their scheduled medical appointments.

For the purpose of study awareness, informational flyers will also be available to patients in the exam rooms, waiting rooms, and through Oncology Care's MDC (**Attachment X: Recruitment Flyer - Controls**).

Demographic information will be collected on all eligible participants who are asked to participate. This information will be collected as part of the Pre-Treatment Survey for Case

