Dyads and Post-Treatment Survey for Control Dyads. Patients and caregivers that are approached, but decline participation will be asked to complete an anonymous brief demographic survey (**Attachment Z: Non-Participant Survey**).

Providers (GMC only):

Providers will be invited to take part in the study by receiving an invitation e-mail (**Attachment AA: Provider Interview Email Invitation**) from the study team. We will use an opt-out approach when inviting providers to participate. Providers who are not interested in participating are asked to respond to the e-mail invitation within 14 days of receipt. Those who do not respond within the 14-day window will be scheduled for an interview.

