### 4.4.2 Approximate Duration of Study

We anticipate recruitment, consent, and enrollment of 115 Geisinger participants (65 patients and 50 caregivers) to occur over the course of seven (7) months. Patients are able to participate independent of having a caregiver; therefore, the number of Geisinger patients enrolled is reflective of this possibility. Our goal is to include 100 participants in our analysis (50 patients and 50 caregivers) organized as 25 Cases Dyads and 25 Control Dyads. Case and Control Dyads will be in the study for approximately an 8-10-week duration. Their study participation ends once they have completed the post-period survey. The post-period survey may be completed 1-2 weeks post-Oncology Care. We estimate that study participation for all Dyads will end within ten (10) months after recruitment begins.

Providers participation in the study will end once their interview has been completed. Provider interviews will take approximately two (2) months to schedule and complete. We anticipate enrolling up to 20 providers.

As we near the end of data collection, data analysis and reporting of the study findings will begin. We estimate that this work will take approximately six (6) months.

We estimate that the study duration is eighteen (18) months.

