### **Control Dyads:**

[figure not shown]
The research assistant will approach all eligible patients in the clinic to inform them of patient-caregiver study (**Attachment U: RA Talking Points**). Interested patients will be asked to identify a caregiver to participate, however patients can participate in the study regardless of caregiver participation. The dyad will provide consent (**Attachment F: Informed Consent – Control**) (eConsent). At the completion of the control participant's 8-week study period, the dyad will complete the post-period survey (**Attachment C – Post Treatment Survey Patient and Attachment D: Post Treatment Survey Caregiver**) based on their stated format

preference determined during consent - in clinic, electronically or mailed (**Attachment O: Initial Post- Treatment Survey Patient Communication – Control** and **Attachment P: Initial Post Treatment Survey Caregiver Communication – Control**). Patients and/or caregivers that do not complete the survey in one week will receive a reminder to complete the survey (**Attachment Q: Reminder- Post Treatment Patient Communication – Control** and **Attachment R: Reminder – Post Treatment Caregiver Communication – Control**). Three total follow-up attempts will be made to non-responders approximately one week apart; attempts will be made if no data or incomplete data are received with the goal of obtaining completed surveys. Once the study team receives the completed survey, the patient and caregiver will each receive a \$25 gift card. The gift card will be mailed to each individual (**Attachment T: Compensation Letter**). Participants who do not receive a copy of their consent form at the time of consent will be mailed a copy of their consent form for their records (**Attachment BB: Consent Form Letter**).

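### Control Dyads give survey demographics only at the post-period, so a Control caregiver lost before then has no described demographic source and a lost Control patient lacks survey-only items

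*Combined protocol and SAP*

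**What the plan says.** Section 4.3 (Recruitment, Controls) states the intent: "Demographic information will be collected on all eligible participants who are asked to participate". The next sentence, which runs across a page break, sets the timing: "This information will be collected as part of the Pre-Treatment Survey for Case" and then "Dyads and Post-Treatment Survey for Control Dyads". People who are approached and decline are asked for a short anonymous demographic survey (Attachment Z).

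Controls have no earlier survey. Section 3.3 says that for them "questionnaires will be fielded at the post-period only". Section 4.5 (Control Dyads) puts that survey at the end of their participation: "At the completion of the control participant's 8-week study period, the dyad will complete the post-period survey". Section 4.4.2 allows some slack: "The post-period survey may be completed 1-2 weeks post-Oncology Care".

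Other sources exist for patients. Section 4.3 identifies Controls from health-record data so that they "match case patients in terms of sex, age category, lung cancer histology, and lung cancer clinical and/or pathological staging information". The Demographics row of the table in section 4.6 lists the Epic record beside the surveys. Section 4.8.1 lists date of birth, gender, treatment location and problem-list diagnoses separately from survey responses.

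For caregivers, section 4.2.1 closes the health-record route: "If a caregiver receives care at Geisinger, his/her patient-related records are not of interest to or related to this study". Section 4.8.1 lists caregiver age and gender as data elements but names no source for them other than the survey.

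**The concern.** The stated aim is to describe everyone approached, and the schedule cannot achieve it. Cases are asked before they start using the application and decliners are asked at approach. Controls are asked only if they reach and return the last survey, so one who consents and then dies, withdraws or does not respond is never asked.

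This matters because the primary question is a non-randomised comparison made at the post-period only. Section 4.1 justifies that design by expecting no baseline differences between the groups, while acknowledging bias from convenience sites and non-random assignment. With no Control baseline survey, demographics at entry are among the few available checks on that expectation. Matching uses patient characteristics, and remote-caregiver status is matched only where possible. Caregivers nevertheless supply half of each dyad mean and have their own Case-Control contrast (section 4.8.1). A lost Control caregiver would be neither matched on demographics nor described.

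A second, weaker issue is timing. A survey-only item that can change during treatment may be recorded before the study period in Cases and after it in Controls.

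**Working it through.** **1. The plan's own figures (section 4.2.1).** Eligible GMC patients in 12 months: 153. Half for a 6-month period: 153 x 0.5 = 76.5, printed as 77. Consent at 37%: 77 x 0.37 = 28.5, printed as 28. Completion at 90%: 28 x 0.90 = 25.2, printed as 25. These reproduce. The 90% is a Phase II observation from dyads using the application in one clinic. It is not a survey response rate at the control sites.

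**2. Who is asked for survey demographics, and when.**

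| Group | When asked | Asked if lost before the post-survey? |
|---|---|---|
| Case patient, Case caregiver | Baseline | Yes |
| Decliner | At approach | Not applicable |
| Control patient | Post-survey | No; health-record items and matching variables remain |
| Control caregiver | Post-survey | No; no other source described |

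**3. Size of the gap.** Expected Control Dyads lost = n x (1 - completion), with n = 25 (sections 3.3, 4.2.1 and 4.4.2).

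| Completion | Calculation | Caregivers with no demographics | Patients lacking survey-only items |
|---|---|---|---|
| 95% (assumed) | 25 x 0.05 | 1.25 | 1.25 |
| 90% (plan) | 25 x 0.10 | 2.5 | 2.5 |
| 80% (assumed) | 25 x 0.20 | 5 | 5 |
| 70% (assumed) | 25 x 0.30 | 7.5 | 7.5 |

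The table treats each dyad as lost or retained whole. The corresponding Case figure is 0 at every rate, because Case demographics are already in hand.

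**4. Chance that the gap arises at all.** At 10% loss, with dyads lost independently, the probability of at least one lost Control Dyad is 1 - 0.90^25 = 0.93.

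**5. Sensitivity to n.** If 28 Control Dyads were enrolled to yield 25, the expected loss is 28 x 0.10 = 2.8. Section 4.8.2 gives 50 dyads per group, in conflict with the other sections; on that figure it is 50 x 0.10 = 5.

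**The case against.** The strongest reply is that little depends on these data. The primary question compares post-surveys, so a Control without one contributes no survey outcome and its missing demographics change no survey comparison. All tests are described as descriptive, the selection biases are acknowledged, and three follow-up attempts are made for missing or incomplete surveys. This stands, and it limits the impact. It does not remove the point: describing the groups is the purpose of the analysis, and Case caregivers who drop out can be compared with Case completers on survey demographics while Control caregivers cannot.

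A reader might infer three stronger things that the documents do not support:

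- **That lost Controls have no demographics at all, or that Control drop-outs cannot be compared with completers.** This is not so for patients. Age, sex, histology, stage, site and diagnoses remain available from the health record and the matching step.
- **That the groups' descriptors are necessarily taken on opposite sides of the study period.** Attachments C and D serve both groups, and the Demographics row in section 4.6 cites the pre and post surveys. Cases may therefore answer the same items again at post, which would allow a same-time description among completers. The attachments are not available, so neither this nor which items can change can be checked.
- **That the Control delay is a fixed 8 weeks or more.** Section 4.4.1 says Control Dyads may have a shorter study period because they are recruited after Cases.

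Even if Cases repeat the items at post, that does not recover lost Controls or the Control group's status at entry.

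**Conclusion.** The point holds in limited form. The schedule in section 4.3 does not meet its own aim of collecting demographics on everyone approached. At the plan's 90% completion, about 2.5 of 25 Control caregivers would have no described demographic source and about 2.5 of 25 Control patients would lack survey-only items. At an assumed 80% it is about 5 of each. Post-period loss costs the Case group none.

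This rests on 25 Control Dyads, on applying the Phase II rate to control sites where the true loss is unknown, and on there being no undescribed source for caregiver age and gender. The timing difference is possible but unverified. The primary survey comparison is not altered by the gap. What is lost is a description of the Control group as enrolled, and a comparison of completing with lost Control caregivers. It is a worthwhile correction of modest impact.

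**What to change.** Add a short demographic page to the existing Control consent step: in the REDCap eConsent session for those in clinic, and through the consent email (Attachment M) for remote caregivers. Provide the same page with paper consent.

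Leave Attachments C and D as they are. The documents describe one version of each, used by both groups, so removing items would also change the Case post-survey.

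Amend section 4.3 to say that demographics are collected at enrolment in both groups. State in section 4.8.1 that the enrolled groups, and completers versus non-completers within each group, will be described from these enrolment data.

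The cost is a minor IRB amendment, one REDCap page and a few extra minutes for Controls at first contact, with no new visit. It has to be in place before Controls are lost, because a caregiver's answers cannot be recovered afterwards.

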## 4.4 Study Duration

### 4.4.1 Approximate Duration of Subject Participation

Case Dyads (patient and caregiver) will participate in the study for approximately a 10-week duration (study period week 1 (baseline) followed by 7 weeks of intervention and a post-study questionnaire completed by week 10), however Control Dyads may have a shorter study period as they will be identified and recruited after Case Dyads and our intent is to authentically represent an early, 8-week Oncology Care period. The end of the study is the completion of the post-period survey. We anticipate most patients' Oncology Care cycles occurring over an 8-week period, however the post-period survey may be completed 1-2 weeks post-Oncology Care. Providers will be asked to participate in a one-time interview at the post-period when all Case Dyads have completed the study.

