***Observe FCA in clinical oncology practice to evaluate quality and performance indicators.***

Integrate exposure to FCA as standard of care in a conveniently selected clinic for persons with lung cancer and their caregivers. Clinicians in this clinic have contributed to the development and testing of FCA as standard of care at Geisinger Medical Center in Danville, PA (“GMC”). This clinic will serve as the treatment site. Electronic health records and FCA dashboard analytics will be used to evaluate clinician use of the tool. Clinicians at the treatment site will provide interview data describing their experience related to quality, FCA adoption and implementation into workflow integration at the post-period;

### 3.2 Specific Aim 2

***Observe FCA use among patients and caregivers to evaluate quality and performance indicators associated with oncology care.*** From the treatment site, identify, recruit, consent and enroll persons with lung cancer (newly diagnosed or recent recurrence of disease) and their caregivers. Recruitment will continue until 25 patients and 25 caregivers (Case Dyads) are enrolled. Electronic health records for patients (appointment, clinical, and patient-reported data such as the M.D. Anderson Symptom Inventory that is standard of care) and study questionnaires will be used to evaluate quality and performance indicators. Questionnaires will be fielded with Case Dyads, as hereinafter defined, at baseline and after 8 weeks of exposure to FCA. Pre-post changes will be evaluated among cases.

### 3.3 Specific Aim 3

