Coordination of Care	Coordination of Care Establish accountability and negotiate responsibility; communication; information transfer; proactive plan of care; monitoring; support of patient and family self-management goals; teamwork focused on coordination	Patient-Caregiver	Patient and caregiver surveys  Attachments A-D: Patient and Caregiver Pre and Post Survey
	Coordination of Care Adoption of FCA Communicate, monitoring, patient- and caregiver- centered care, efficient, timely	Health Care Provider	Provider Interview Attachment Y: Physician Interview Guide
	Coordination of Care Health care utilization (scheduled vs. missed)		Epic EHR and Aria

	appointments, hospital admissions, ED visits), costs	Health System Representative	See section 4.8.1
	
Adoption Proportion of patients and families adopting and using app
	Health System Representative	
Epic patient lists, recruitment records, and FCA usage data
 
Patient Survey Attachment A and C: Pre and Post Survey
 
Caregiver Survey Attachment B and D: Pre and Post Survey

Demographics	
Collection of standard demographics variables
	
Patient-Caregiver Health Care Provider
	
Patient Survey Attachment A and C: Pre and Post Survey
 
Caregiver Survey Attachment B and D: Pre and Post Survey
 
Epic HER See section 4.8.1
 
FCA Metrics See section 4.8.1
 
Human Resources See section 4.8.1

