### 4.8.1 Statistical Analysis Plan

The study team will describe quality and performance indicators observed among study participants and evaluate associations between 1) difference in quality of care (satisfaction, quality of life, burden, coordinated care) associated with FCA exposure (Case Dyads vs. Control Dyads, Post-Treatment Surveys only); and 2) change in quality of care (satisfaction, quality of life, burden, coordinated care) associated with FCA use (Case Dyads Pre-Treatment Surveys vs. Post-Treatment Surveys).

Case Dyads and Control Dyads demographic and clinical information and survey responses will be fully described using frequencies and percentages for categorical variables and mean and standard deviation or median and interquartile range for continuous variables distribution dependent. To evaluate the difference in quality of care associated with FCA **exposure** (Case v. Control) will be evaluated using chi-square test, t-tests and non-parametric univariate tests distribution dependent. Mean patient and caregiver scores will be calculated for each dyad and compared between groups. Sensitivity analyses may stratify by level of FCA use (low-moderate-high) per dyad and opportunity time for FCA exposure. Case to Control patient analyses and Case to Control caregiver analyses will also be performed to detect role-level differences in perceptions of quality and performance associated with FCA exposure. To evaluate the association of the change in quality of care associated with FCA **use** difference in response between pre- and post- surveys paired t-test or ANCOVA depending on data type and distribution. Within Case Dyads, patient means will be compared with caregiver means to detect difference in quality and performance perceptions based on role.

All statistical analyses will be performed using SAS v9.4 (SAS Institute, Inc., Cary, NC, USA). All statistical tests are meant to be descriptive since this is purely an exploratory analysis.

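### Case and Control Dyads have no common time origin or observation window, so part of any post-period difference could reflect time rather than FCA

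*Combined protocol and SAP*

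**What the plan says.** Section 4.4.1 gives Case Dyads about ten weeks, made up of "study period week 1 (baseline) followed by 7 weeks of intervention and a post-study questionnaire completed by week 10". The same sentence adds that "Control Dyads may have a shorter study period as they will be identified and recruited after Case Dyads", and ends by explaining that "our intent is to authentically represent an early, 8-week Oncology Care period". It sets no minimum Control period.

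Other sections read differently. Section 4.4.2 gives 8 to 10 weeks for both groups. Section 4.5 surveys Case Dyads at the end of eight weeks, and for Controls it refers to the participant's "8-week study period, the dyad will complete the post-period survey". Both groups may then receive up to three reminders about a week apart. None of these sections states a start date for the count. Section 4.2.2 admits patients before treatment begins or up to 27 days after it has begun.

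The primary question in Section 4.6 is the post-period difference between Case and Control Dyads. Its table includes health care utilisation, listed as "appointments, hospital admissions, ED visits), costs", with no period or denominator. Under Section 4.8.1 the Case-Control difference "will be evaluated using chi-square test, t-tests and non-parametric univariate tests distribution dependent". Time appears only as an optional sensitivity stratification, by how long a dyad had the opportunity to use FCA.

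**The concern.** Admissions, ED visits, appointments and costs accumulate with time. If one group is watched for longer, its totals are higher even when the weekly rates are equal. With Cases as the longer group, the false direction would be more utilisation with FCA.

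Survey scores do not accumulate, but satisfaction, burden and quality of life can move over an intense treatment course. Surveys taken at different times since the start of treatment are therefore not like for like. Controls complete no baseline survey, so a timing effect cannot be checked against their starting scores.

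The optional stratification does not help. Controls have no FCA exposure, so stratifying on it cannot equalise observation time between the groups. Section 4.1 is candid about several sources of bias, but unequal observation time is not among them.

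**Working it through.** **1. The plan's own figure.** Section 4.4.1: 1 baseline week + 7 weeks = 8 weeks. Adding up to 2 weeks for the survey gives 8 + 2 = 10 weeks, which reproduces the stated Case duration of about 10 weeks.

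**2. Counts at equal event rates.** Expected count = weekly rate × weeks observed, so with equal rates the Case:Control ratio is Case weeks ÷ Control weeks.

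- Both groups at the 8 weeks of Section 4.5: 8/8 = 1.00.
- Case total from Section 4.4.1 against Control period from Section 4.5: 10/8 = 1.25.
- Shorter Control periods, which are assumptions because the documents give no minimum: 10/7 = 1.43 and 10/6 = 1.67.

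**3. What this does to a t-test.** The inputs were 25 against 25 (the analysis goal in Section 4.2.1), no true effect, 20,000 simulated studies, and a two-sided t-test at an assumed 0.05. The documents give no event rates, so the weekly rates below are assumptions. Overdispersed means gamma-Poisson with shape 2. Entries are the percentage of studies showing a false difference on raw counts, with the result per week observed in brackets.

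| Weekly rate | 8 v 8 weeks | 10 v 8 weeks | 10 v 6 weeks (assumed) |
|---|---|---|---|
| 0.05, Poisson | 5.1 (5.1) | 7.8 (4.7) | 19.1 (5.3) |
| 0.5, Poisson | 5.1 (5.1) | 37.5 (5.0) | 93.8 (5.3) |
| 0.5, overdispersed | 5.0 (5.0) | 13.5 (4.8) | 50.9 (4.9) |
| 2, Poisson | 5.2 (5.2) | 90.1 (5.2) | 100.0 (4.8) |
| 2, overdispersed | 4.9 (4.9) | 17.4 (4.8) | 63.0 (5.0) |

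Equal windows, or counts per week, bring the false-difference rate back to about 5%.

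**4. Time on care.** Take 27 days as the latest entry and 8 weeks = 56 days.

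- If the 8 weeks run from enrolment, a patient entering on day 0 of treatment is surveyed at 56/7 = 8.0 weeks of care, and one entering on day 27 at (27 + 56)/7 = 11.9 weeks.
- If the 8 weeks run from the start of treatment, both are surveyed at 8 weeks of care, but the day-27 patient has been in the study for only (56 − 27)/7 = 4.1 weeks.

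These are extremes for single patients, not group means. The entry limit is the same in both groups, so a group difference arises only if entry times are distributed differently or the two groups are counted from different origins. The calculation shows that neither origin aligns both observation length and time on care.

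**5. Outcomes to which the ratios do not apply.** If appointments are analysed as missed out of scheduled, numerator and denominator grow together and the proportion need not change with the window. For survey scores the documents give nothing from which to compute a timing effect.

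**The case against.** The strongest reply is that the groups may in fact be aligned. Section 4.4.1 ties the shorter Control period to representing the first eight weeks of care, and Section 4.5 surveys both groups after eight weeks. On that reading Controls spend less time in the study but are measured at a comparable point of treatment, and the count ratio is 1.0. The 10-against-8 comparison also sets a Case duration that includes time to return the survey against a Control duration that does not. These points stand: the imbalance is possible, not established.

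Four stronger claims are tempting, and the documents do not support them.

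- A reader might infer that time on study is counted from enrolment. No section says so. Recruiting Controls after their matched Cases fixes calendar order, not how far into treatment a Control is.
- A reader might see a conflict between Section 3.2, which surveys Cases "at baseline and after 8 weeks of exposure to FCA", and the seven weeks of intervention in Section 4.4.1. The baseline week plus seven is eight, so there is no conflict to press.
- A reader might take it as settled that utilisation will be tested on raw counts. Section 4.8.1 describes the exposure comparison in terms of post-treatment surveys only. Applying its univariate tests to utilisation is an inference from the table in Section 4.6, because no utilisation analysis is written.
- A reader might carry the ratios over to missed appointments. If these are a proportion, the ratios do not apply.

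It is also fair that Section 4.8.1 calls every test descriptive. That lowers the consequence, but it does not remove bias from the difference being described, and Section 4.7 expects later studies to build on these findings.

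**Conclusion.** The point holds as a gap that can produce bias, not as a demonstrated bias. Section 4.4.1 allows a shorter Control period, Sections 4.4.2 and 4.5 imply similar periods, no time origin is stated, and nothing in the planned comparison accounts for time.

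The size cannot be fixed from the documents. At equal event rates the count ratio runs from 1.0 to 1.25 on the stated durations, and the values of 1.43 and 1.67 rest on assumed Control periods. The false-difference rates rest further on assumed event rates and significance level. A reader might infer that the bias certainly enters the primary comparison at 1.25 or more. The documents do not support that, since the like-for-like reading gives 1.0. The correction is cheap and should be made before data are extracted.

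**What to change.** - Reconcile Sections 4.4.1, 4.4.2 and 4.5, and state for each group the date from which the study period is counted and when it ends.
- Extract EHR and Aria utilisation for every patient in both groups over one fixed window from the start of treatment, censored at death, or analyse it as a rate per person-time. Encounter dates and date of death are already in the Section 4.8.1 data list, so this can be done retrospectively. A window from the start of treatment will include some time before FCA was activated for Cases who enter late. The SAP should say so, because it dilutes any FCA effect.
- State whether appointments are analysed as counts or as the proportion missed.
- Add the treatment start date and the survey completion date to the data elements. Neither is itemised now, although eligibility checking already requires the first.
- Report time from treatment start to post-survey by group, and add a sensitivity analysis that adjusts the survey comparisons for it.

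The cost is SAP wording, two date fields and slightly more analysis.
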